3 HYPOTHESIS

The study hypothesis is that there will be a higher rate of tear evaporation with CL wear compared to when CLs are not worn.

There will also be a significant difference in the rate of tear evaporation of DAILIES TOTAL1 (DT1) and Biotrue ONEday (BOD) after a minimum of 6 hours of CL wear.

There will also be a higher rate of tear evaporation in symptomatic contact lens wearers compared to asymptomatic lens wearers.

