4.1.2 RANDOMIZATION

A randomization schedule will be generated using a web-based program: (www.randomization.com). Participants will be randomized to the type of contact lens to be worn in each eye at Visit 2. A separate randomization will be generated for symptomatic and asymptomatic participants. The final study randomization schedule will be generated by CORE's Database Administrator, and provided to the research assistants for the study. Study investigators will remain masked to the randomization schedule until the interim data analysis. Study investigators will be granted access to the randomization schedule for the first 10 symptomatic and 10 asymptomatic participants in order to conduct the interim data analysis. Following

calculation of the sample size required to complete the study, study investigators will remain masked to the remainder of the randomization schedule until the study is completed and the database is locked.

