4.2 STUDY POPULATION

4.2.1 SAMPLE SIZE CALCULATION

Because this is a pilot study, a sample size calculation has not been completed. An interim data analysis will be undertaken after 20 participants (10 symptomatic and 10 asymptomatic) have completed the study. The results of the interim data analysis will be used to calculate a sample size using G*Power.

A p-value of < 0.05 will be considered statistically significant.

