4.4.3 VISIT 2: BASELINE AND DISPENSING VISIT

- Participants will attend the visit having been awake for at least 2 hours.
- Participants will not have worn any contact lenses, used any eye drops or artificial tears, or worn any eye makeup on the day of the visit. Participants who have worn lenses, used eye drops, used artificial tears, or worn eye makeup on the day of the visit will be rescheduled.
- Monocular and binocular logMAR visual acuity will be recorded with high contrast letters under high illumination with spectacles or spectacle refraction.
- Slit lamp biomicroscopy using white light.

The participant will be assigned a randomization ID in order to determine which type of CL will be inserted into each eye.

Participants will be required to adapt to the room environment for at least 15 minutes prior to reporting subjective monocular ratings and performing baseline evaporimetry measurements. The

participant will apply thin layer of petroleum jelly will be applied to the skin surrounding the eye using a cotton tipped applicator to minimize the amount of evaporation from the skin.

- The participant will be asked to give subjective monocular ratings for:
 - Comfort
 - Dryness
 - Burning or stinging
- Baseline evaporimetry measurements without contact lenses
- Non-invasive pre-ocular tear film break up time (Tearscope)
- Lipid layer thickness (Tearscope)
- Lipid layer thickness (LipiView II)
- Evaporimetry measurements will be repeated at least 15 minutes after the initial baseline measurement.
- Non-invasive pre-ocular tear film break up time (Tearscope)
- Lipid layer thickness (Tearscope)
- Lipid layer thickness (LipiView II)
- The participant will wipe away petroleum jelly from skin surrounding the ocular surface using a tissue.
- Contact lenses will be given to the participants in a masked manner (Section 4.3.7).
- The study contact lenses will be inserted by the participant.
- The lenses will be allowed to settle for at least 15 minutes.
- The participant will apply a thin layer of petroleum jelly will be applied to the skin surrounding the eye using a cotton tipped applicator to minimize the amount of evaporation from the skin.
- The participant will be asked to give subjective monocular ratings for:
 - Comfort
 - Dryness
 - Burning or stinging
- Baseline evaporimetry measurements with contact lenses.
- Non-invasive pre-lens tear film break up time (Tearscope)
- Lipid layer thickness (Tearscope)
- Lipid layer thickness (LipiView II)

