4.4.4 VISIT 3: FOLLOW UP & STUDY EXIT

Participants will attend the visit having not used any eye drops or eye makeup on the day of the visit.

- Monocular and binocular logMAR visual acuity will be recorded with high contrast letters under high illumination.
- Contact lens fit will be assessed.

Participants will be required to adapt to the room environment for at least 15 minutes prior to reporting subjective monocular ratings and performing evaporimetry measurements. The participant will apply thin layer of petroleum jelly will be applied to the skin surrounding the eye using a cotton tipped applicator to minimize the amount of evaporation from the skin.

- The participant will be asked to give subjective monocular ratings for:
 - Comfort
 - Dryness
 - Burning or stinging
- Evaporimetry measurements with contact lenses. Evaporimetry measurements will not be taken until the study lenses have been worn for a minimum of 6 hours.
- Non-invasive pre-lens tear film break up time (Tearscope)
- Lipid layer thickness (Tearscope)
- Lipid layer thickness (LipiView II)
- The participant will wipe away petroleum jelly from the skin surrounding the ocular surface using a tissue.
- Contact lens removal.
- Slit lamp biomicroscopy.
- Exit monocular and binocular logMAR visual acuity will be recorded with high contrast letters under high illumination with spectacles or spectacle refraction.

Study Exit

- The study exit form will be completed when a participant exits the study. This will occur either at study completion, or if the participant is discontinued from the study at another time. A study exit form must be completed for all participants who have been given a study number. If in the opinion of the investigator post-study follow-up visits are required, the exit form will be completed after the last follow-up visit.
- The participant will be discharged and will sign the study completion forms and receive remuneration for participating in the study.

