10 STATISTICAL ANALYSIS AND DATA MANAGEMENT

10.1 STATISTICAL ANALYSIS

All data will be analyzed by CORE at the University of Waterloo on unmasked data using Microsoft Excel and statistical analysis software such as GraphPad and SPSS. Interim data analysis will be conducted after 10 symptomatic and 10 asymptomatic participants have completed the study to determine the optimal time period over which to calculate the slope. The results of the interim data analysis will also be used to calculate the sample size.

Descriptive statistics will be provided on information regarding baseline variables (age, sex, contact lens refractive error distribution, etc.). Data may be evaluated for individual groups

(asymptomatic versus symptomatic) and when both groups are combined. Data will be tested for normality of distribution using Shapiro-Wilk tests. A p -value of < 0.05 will be considered statistically significant. Additional analysis may be conducted.

Table 4 lists the primary outcome variables and anticipated statistical procedures.

Table 4: Outcome variables and anticipated statistical procedures

| Variable | Analysis | Statistical test |
|--------------------------------------------------------------------------------------------------------------------------------------------------------------|--------------------------------------------------------------------------------------------------------------------|--------------------------------------------------------------------------------------------------------------------|
| Tear evaporation rate | Change in relative humidity over time | Slope |
| Tear evaporation rate/Time | Effect of lens type | RMANOVA Mauchly's test of sphericity Greenhouse-Geisser p values Tukey HSD post hoc Paired t -test |
| Tear evaporation rate/ Subjective ratings/Non- invasive breakup time/Lp d ayer thickness (Lp View II - continuous)/Area of the ocular surface | Relationship between tear evaporation rate and subjective comfort and dryness/other tear film assessments | Pearson correlation – r |
| Tear evaporation rate/ Lp d ayer thickness (Tearscope - ordinal)/ Volume of the goggle | Relationship between tear evaporation rate and lpdayer thickness | Spearman correlation – ρ |

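### Table 4 names no baseline covariate for the 6-hour DT1-BOD comparison; regressing the Visit 3 eye difference on the no-lens eye difference would be a cheap but conditional precision gain

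*Combined protocol and SAP*

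**What the plan says.** Section 3 expects DT1 to differ from "BOD) after a minimum of 6 hours of CL wear". Only Visit 3 can supply that comparison; Section 4.4.4 states: "Evaporimetry measurements will not be taken until the study lenses have been worn for a minimum of 6 hours".

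Section 4.4.3 schedules a baseline evaporimetry session without lenses and then a second one before insertion: "Evaporimetry measurements will be repeated at least 15 minutes after the initial baseline measurement". A third Visit 2 session follows once the lenses have settled. Under Section 4.5.16 each session gives a rate for each eye.

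The Table 4 row for evaporation rate over time and effect of lens type lists RMANOVA, Mauchly's test and "Greenhouse-Geisser p values Tukey HSD post hoc Paired t -test". It names no covariate and no change score, does not list the Time levels, and does not say which term or session decides the lens hypothesis.

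The interim look after 10 + 10 completers is also meant "to determine the optimal time period over which to calculate the slope", and Section 4.2.1 adds: "The results of the interim data analysis will be used to calculate a sample size using G*Power". For that look, Section 4.1.2 provides: "Study investigators will be granted access to the randomization schedule for the first 10 symptomatic and 10 asymptomatic participants".

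**The concern.** Wearing one lens in each eye removes variation between people. It does not remove a stable difference between a participant's two eyes. The protocol gives reasons why one could exist: each goggle lens has its own sensor (Section 1), and ocular surface area and goggle volume are measured eye by eye (Sections 4.5.10 and 4.5.11). Subtracting the closed-eye rate removes skin evaporation, but not a factor that scales the humidity slope. Any such difference would appear in both the no-lens and the 6-hour eye differences, and a Visit 3 paired t-test leaves it in the error term.

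The data to remove it are collected anyway, and the completion target is only 20 pairs of eyes. Timing matters as well: several candidate tests are listed, and the investigators will see lens allocation for the first 20 completers at the interim.

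**Working it through.** The plan states no power, effect size or SD, so there is no figure of its own to reproduce.

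**Inputs from the documents.** n = 20 pairs (Section 4.2.2, minimum target); significance at 0.05 (Section 4.2.1), taken as two-sided; two no-lens and two lens-on sessions.

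**Assumptions.** Eye differences (DT1 eye minus BOD eye) have equal SD, set to 1. rho is the correlation between one no-lens eye difference and the 6-hour eye difference; the documents do not give it, so a range is shown. The effect is the one giving the Visit 3 paired t-test 80% power at n = 20, which is 0.660 SD.

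**Covariate.** The covariate is the mean of the two no-lens eye differences. If these correlate b with each other, its correlation with the 6-hour difference is r = rho × sqrt(2/(1+b)), so r² = 2rho²/(1+b). Relative to the paired t-test, the variance is about (1 − r²)(n − 2)/(n − 3), on n − 2 degrees of freedom.
- rho = 0: 18/17 = 1.059, a small loss.
- rho = 0.5, b = 0.8: r² = 0.5/1.8 = 0.278; 0.722 × 1.059 = 0.765.
- rho = 0.5, b = 0.5: r² = 0.5/1.5 = 0.333; 0.667 × 1.059 = 0.706.

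Break-even, allowing for the lost degree of freedom, is r = 0.25 at n = 20, 0.39 at n = 10 and 0.15 at n = 50. For a single session, r = 0.25 at n = 20 corresponds to rho of about 0.24 when b = 0.8 (0.25/1.054) and about 0.19 when all correlations are equal (0.19 × sqrt(2/1.19) = 0.25).

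**Power (%) at n = 20, by simulation.** Lens-by-time uses Greenhouse-Geisser with the effect at both lens-on sessions. In the b = 0.8 rows the two lens-on sessions also correlate 0.8.

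| Case | rho | Paired t | Covariate | Change score | Lens-by-time |
|---|---|---|---|---|---|
| b = 0.8 | 0 | 80 | 77 | 53 | 55 |
| | 0.2 | 80 | 79 | 63 | 66 |
| | 0.3 | 80 | 82 | 69 | 72 |
| | 0.5 | 80 | 89 | 84 | 87 |
| | 0.7 | 80 | 98 | 98 | 99 |
| all equal | 0 | 80 | 78 | 63 | 63 |
| | 0.3 | 80 | 83 | 78 | 81 |
| | 0.5 | 80 | 91 | 90 | 93 |
| | 0.7 | 80 | 98.5 | 99 | 99.5 |

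If the effect is present only at 6 hours, lens-by-time falls to 47 / 60 / 69 / 87 / 98% in the b = 0.8 rows. With equal correlations of 0.5 it is 82-83%, against 91% for the covariate.

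**Participants for 80% power with the covariate** (paired t-test: 20). b = 0.8: 22 / 21 / 20 / 17 / 12. Equal correlations: 22 / 19 / 16 / 11.

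**Main-effect dilution.** Averaged over four sessions, an effect d at both lens-on sessions becomes 2d/4 = d/2; an effect only at 6 hours becomes d/4. With equal correlations the variance of the average is (1 + 3rho)/4. At rho = 0.5 that is 0.625 (SD 0.791), so the standardized effect is 0.330/0.791 = 0.42 or 0.165/0.791 = 0.21, against 0.66 at Visit 3. At rho = 0 with the effect at both lens-on sessions it is 0.330/0.5 = 0.66: the estimate is still halved, but power is not lost.

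**False-positive rate.** The uncentred intercept test rejects in 4.9-5.1% of null simulations. If the covariate is centred at its sample mean, the rate is 7 / 10 / 19% at rho 0.3 / 0.5 / 0.7 (equal correlations), because the intercept then tests the unadjusted mean difference against the smaller residual error.

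**The case against.** A reader might infer that the baseline data are left unused. The documents do not show that. Sphericity matters only for a within-participant factor with three or more levels. Lens type has two, and there are only two lens-on sessions, so a Time factor that needs Mauchly's test would include a no-lens session. If the factor were instead no lens, DT1 and BOD, the no-lens data would still enter. The objective in Section 2 is also a before-and-after comparison. This is inference, since the levels are not listed and software may print Mauchly's test by default, but it is the likelier reading.

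It follows that the fair comparator is the better of the two listed tests. On the table above, the covariate then differs by −3, −1, +2, +2 and −1 points (b = 0.8) and by −2, +2, −2 and −1 points (equal correlations). This stands, with two limits: which listed test is better is not known beforehand, and where the effect appears only at 6 hours the covariate can gain more (91% against 82-83%).

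It is also fair that rho may be low. The goggle is hand-held and re-applied for each reading, and a pre-ocular rate is being used to predict a pre-lens rate at least 6 hours later. Section 10.1 allows each symptom group to be analysed separately. At n = 10, for an effect giving the paired t-test 80% power, the covariate gives about 74% at rho 0 and 78% at 0.3 (b = 0.8).

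Finally, this is a pilot with no power claim, and its procedures are described as anticipated. That limits the weight of the point but does not remove it.

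**Conclusion.** The point holds as a minor improvement in precision and prespecification. No covariate is named, the deciding term is not stated, and one available reading (a lens main effect over all sessions) would shrink the 6-hour estimate to a half or a quarter.

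Two stronger conclusions are not supported. The listed paired t-test at Visit 3 is not biased or invalid; it tests the stated hypothesis without dilution. Nor is a gain assured: it needs a persistent between-eye difference, whose size the documents do not give. The power figures rest on the assumed rho, equal SDs, n = 20 and the 80% anchor, which is a device of this check and not a claim of the plan. The case for the covariate is that it loses little when rho is low, unlike the change score or lens-by-time, and roughly matches lens-by-time when rho is 0.5 or more.

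**What to change.** Before the interim unmasking, state in Section 10.1 that the lens hypothesis is tested by regressing the Visit 3 eye difference (DT1 minus BOD) on the same eyes' mean no-lens difference from the two Visit 2 baselines, using the same slope window. The lens effect is the intercept at zero baseline difference, with the covariate left uncentred. The settled-lens reading at Visit 2 should not be used as the covariate, because it is taken after the randomized lens is in the eye.

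Keep the unadjusted Visit 3 paired t-test as a sensitivity analysis and the RMANOVA as supportive, with its Time levels listed. Do not decide the hypothesis on a lens main effect that includes no-lens sessions. If the lens hypothesis is the one that sets the sample size, enter effect divided by this test's residual SD in G*Power (one-sample t) and add 1-2 participants for the estimated slope.

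The cost is wording and one degree of freedom: 2-3 points of power, or about 2 more participants, if rho is zero. No new measurement is needed. The change does not settle the choice of slope window, which is still made at the interim.

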10.2 DATA MANAGEMENT

Data from this study will be retained by CORE for a minimum of 25 years on a password-protected server. After 25 years, data will be disposed of in accordance with the guidelines laid out by the University of Waterloo.

10.3 COMMENTS ON SOURCE DOCUMENTS

Data analysis will not be conducted on comments which have been recorded in the source documents. Only relevant and applicable comments will be included in the final report as deemed necessary by the lead investigator.

11 PROTOCOL TRAINING

All study personnel will be required to complete training prior to their involvement in the study. A series of training modules will be developed for the study and records of training will be kept at CORE.

12 STUDY MONITORING

Study monitoring will be conducted by CORE personnel. Consent documentation will be reviewed by a person not involved in the consent process. To improve data integrity, data entry will be double-entered and the entries will be compared for discrepancies. All adverse events and protocol deviations will be reviewed by the Lead Investigator. All serious adverse events and major protocol deviations will be reviewed by the Principal Investigator.

13 STUDY MANAGEMENT

13.1 STATEMENT OF COMPLIANCE

This clinical study is designed to be in compliance with the ethical principles in the Declaration of Helsinki, with the ICH guidelines for Good Clinical Practice (GCP), with the University of Waterloo's Guidelines for Research with Human Participants and with the Tri-Council Policy Statement: Ethical Conduct for Research Involving Humans, 2nd Edition.

- Declaration of Helsinki
- ICH E6 - International Conference on Harmonisation; Good Clinical Practice
- <http://iris.uwaterloo.ca/ethics/human/guidelines/index.htm>
- <http://iris.uwaterloo.ca/ethics/human/ethicsReview/UWStatement.htm>
- <http://www.pre.ethics.gc.ca/eng/policy-politique/initiatives/tcps2-eptc2/Default/>

13.2 ETHICS REVIEW

This protocol will be submitted to and reviewed through the Office of Research Ethics (ORE) at the University of Waterloo. Notification of ethics clearance of the application is required prior to the commencement of the study.

13.3 CLINICAL TRIAL REGISTRATION

The study will be registered with clinicaltrials.gov.

13.4 PROTOCOL DEVIATIONS

Protocol deviations are unanticipated or unintentional changes to a study after it has received prior sponsor approval and ethics clearance. Protocol deviations can be major or minor.

13.4.1 MAJOR PROTOCOL DEVIATIONS

Major protocol deviations may impact the research protocol, information consent document or other study materials, usually cannot be anticipated ahead of time and are often necessary to ensure the safety and welfare of the participants.

The following are examples of protocol deviations that must be reported to the ORE:

- Changes in procedures initiated to eliminate immediate risks/hazards to participants;
- Enrollment of participants outside the protocol inclusion/exclusion criteria whether agreed to or not by the sponsor;
- Medication / device / intervention errors (i.e. incorrect drug or dosage of drug / incorrect contact lens(es) dispensed / incorrect care system dispensed);
- Inadvertent deviation in specific research intervention procedures or timing of the research intervention which could impact upon the safety or efficacy of the study-related intervention or upon the experimental design;
- Information consent documentation violations: no documentation of informed consent; incorrect version of, or incomplete, informed consent documentation used.

13.4.2 MINOR PROTOCOL DEVIATIONS

Protocol deviations caused by or which originate with research participants are considered minor, and normally are not reported to the ORE unless these result in increased risk to the participant(s).

The following are examples of protocol deviations that are considered minor and do not require reporting to the ORE:

- Logistical or administrative aspects of the study (e.g., study participant missed appointment, change in appointment date);
- Inadvertent deviation in specific research intervention procedures or timing of the research intervention which would not impact upon the safety or efficacy of the study-related intervention or upon the experimental design (i.e., missing a measurement during a session that is not considered critical for the study).

13.4.3 REPORTING AND DOCUMENTING PROTOCOL DEVIATIONS

Major protocol deviations must be reported to the ORE within 7 days of the deviation occurring (or its discovery) using the Protocol Deviation Report Form 107 (PDRF). Information from the PDRF is provided to the Clinical Research Ethics Committee (CREC) at the next monthly meeting.

All protocol deviations (major and minor) occurring during the study will be documented and included in the final report.

13.5 PREMATURE TERMINATION OF THE STUDY

CORE or the Office of Research Ethics at the University of Waterloo may terminate the study at any time for any reason.

13.6 STUDY PARTICIPANT RECORDS

Study participant records will be completed to comply with GCP guidelines. Records will contain:

- Unique study acronym and/or code;
- Participant ID;
- Date enrolled;
- Confirmation by investigator that participant met eligibility criteria;
- Confirmation that participant received a signed and dated copy of informed consent;
- Exit date;
- Investigator's signature confirming study exit.

13.7 RETENTION OF STUDY RECORDS AND DATA

Records and data from this study will be retained for a minimum of 25 years. Details regarding storage procedures are given in CORE SOP014_v02 Clinical data management.

14 REPORT

A report will be generated after completion of the study. An internal reviewer will review the report.

